### **6.9.7 Clinical Laboratory Adverse Events**

Clinical laboratory values (other than pregnancy tests results) that are noted as abnormal and clinically significant at study exit and that are changes from Screening values will be documented as AEs.

### **6.9.8 Serious Adverse Events, Serious Adverse Reactions or Suspected Unexpected Serious Adverse Reactions**

#### **6.9.8.1 Reporting SAEs or SARs**

An Investigator must immediately (i.e., within 24 hours) report any SAE or SAR (see Section 6.9.2 for definitions) to the Sponsor or its CRO representative, whether or not considered study intervention-related, including those listed in the protocol or Investigator's Brochure. The Investigator must use the SAE report form and include an assessment of whether there is a reasonable possibility that the drug caused the event. The Investigator must report any SAE or SAR that occurs or is observed during the study. In case of incomplete information, the Investigator must provide follow-up information as soon as possible, again using the SAE report form. The email or fax to submit the SAE report is found in Section 6.9.8.3.

SAE reports will be evaluated by the Medical Monitor. Regulatory authorities, IRB, and Investigators at each of the study sites will be informed as required.

#### **6.9.8.2 Reporting Suspected Unexpected Serious Adverse Reactions (SUSARs)**

The Investigator must immediately (i.e., within 24 hours) report SUSARs. In the event of SUSAR, the site must notify the Medical Monitor (Section 10.2) for the study and submit an SAE report form within 24 hours of notification, observation, or occurrence of the SUSAR, whether or not complete information is available. In the case of incomplete information, the Investigator must provide follow-up information as soon as possible using the SAE report form.

### 6.10 Participant Discontinuation/Withdrawal from the Study

A subject may exit the study by their own volition or at the discretion of the Investigator or the Medical Monitor. Any subject may decide to voluntarily withdraw from the study at any time without prejudice.

The subject may also be discontinued from the study for the following reasons:

- AEs (AEs including, in the opinion of the Investigator, clinically relevant laboratory abnormalities, and intercurrent diseases reported by the subject or observed by the Investigator with documentation on the eCRF)
- Withdrawal of Consent
- Non-compliance (e.g., non-adherence to scheduled follow-up visits or use of study intervention)
- Lost to Follow-up
- Disallowed Concurrent Treatment
- Investigator Decision
- Protocol Deviation
- Death
- Does not meet entry criteria
- Other

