## 2.3 Estimands

### 2.3.1 ESTIMAND 1 (PRIMARY ESTIMAND)

The primary comparison will be based on the ITT population targeting the treatment effect attributable to the randomly assigned treatment, regardless of compliance to study treatment and assuming subjects who discontinued due to lack of efficacy, AEs, or disallowed concurrent treatments follow the behavior of subjects in the reference arm for the duration of the study and subjects who discontinued for other reasons (outside of lack of efficacy, AEs or use of disallowed treatment) would follow the behavior of subjects who are still in the study under same randomly assigned treatment.

- Population: subjects in the ITT population with DED defined through enrollment criteria
- Endpoint:
  - Proportion of subjects with  $\geq 10$  mm increase in unanesthetized Schirmer score on Day 14
- Intercurrent event:
  - Non-optimal treatment compliance is ignored. [treatment policy strategy]
  - Withdrawal due to lack of efficacy, AEs, or disallowed concurrent treatment - multiple imputations using vehicle treatment group regardless of randomized treatment group is used to impute missing data. [hypothetical strategy, missing not at random]
  - Withdrawal due to reasons other than lack of efficacy, AEs, or disallowed concurrent treatment - multiple imputations using randomized treatment is used to impute missing data. [hypothetical strategy, missing at random]

- Population-level summary:
  - Difference in the proportion of subjects with  $\geq 10$  mm increase in unanesthetized Schirmer score on Day 14 between AR-15512 (0.003%) and vehicle

[figure not shown]

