## **7. Analysis Populations**

### **7.1 Intent-to-Treat**

The Intent-to-Treat (ITT) population includes all randomized subjects. The primary efficacy analysis will be performed on the ITT population. Subjects in the ITT will be analyzed as randomized.

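### Protocol 6.10 lets a site end a poor complier's study participation, and with it efficacy data collection, although Estimand 1 targets the effect regardless of compliance

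*Protocol*

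**What the plan says.** Protocol 6.10 allows a subject to leave "at the discretion of the Investigator or the Medical Monitor" and lists reasons for which a subject may be discontinued from the study, not merely from study drug. They include "Non-compliance (e.g., non-adherence to scheduled follow-up visits or use of study intervention", protocol deviation and "Does not meet entry criteria".

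For subjects discontinued for non-compliance, Protocol 6.10.1 asks for one final visit with the Early Termination examinations. Protocol 7.3 and Appendix 1 list safety procedures for that visit; the Schirmer test, SANDE and the symptom VAS are not among them. SAP 8.5 presents Early Termination data in listings only.

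SAP 2.3.1 defines the target as the effect of assigned treatment "regardless of compliance to study treatment". Its intercurrent-event list says "Non-optimal treatment compliance is ignored. [treatment policy strategy". For withdrawals other than those for lack of efficacy, adverse events or disallowed treatment, it says "multiple imputations using randomized treatment is used to impute missing data. [hypothetical strategy, missing at random". SAP 7.1 adds: "The Intent-to-Treat (ITT) population includes all randomized subjects". SAP 1 gives the SAP precedence over the protocol on statistical methods.

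**The concern.** A treatment policy strategy for compliance works only if poor compliers go on being measured. Under 6.10 two subjects with the same dosing record can be handled differently. One is kept, and the observed score is analysed. The other is removed, measurement stops, and the score is imputed as if the subject resembled those still in the study on the same arm. No criterion is given for choosing between the two, so site practice partly decides which question is answered.

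If removed active-arm subjects would in truth have done worse than the rest of their arm, same-arm imputation favours AR-15512, chiefly on SANDE Day 28 and the Day 90 symptom scores. Removal for a deviation or for ineligibility raises a related point. It does not touch the compliance clause, but it sits poorly with an all-randomised ITT set, because a subject stays in the analysis while the data are allowed to lapse.

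**Working it through.** **Inputs.** From SAP 5: 202 per arm for power, 230 per arm randomised, 10% dropout, 80% against 30% responders, SANDE difference 8.3 in absolute value, SD 17.72, two-sided alpha 0.05. Protocol 9.2 gives 7.9 for the SANDE difference. The share of the active arm removed for these reasons, w, is not given; 1% to 5% is my assumption.

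**1. The plan's own figures reproduce.**
- SANDE at 202 per arm: standard error = 17.72 × √(2/202) = 1.763. With 8.3, 8.3/1.763 − 1.96 = 2.75, so power is 99.7%. With 7.9 it is 99.4%. Stated: 99%.
- Primary at 202 per arm: power above 99.99%. Stated: 99%.
- Randomised: 202/0.9 = 224.4, so 225 per arm or 450, against about 460 stated. 460 × 0.9 = 414, the completers in Protocol 4.1.

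**2. The path of a poor complier.**

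| Step | Kept in study | Removed under 6.10 |
|---|---|---|
| Compliance record | Deviation recorded (Protocol 5.6, SAP 12.1) | Same |
| Later Schirmer, SANDE, VAS | Collected at scheduled visits | Not collected (Protocol 6.10.1, 7.3, Appendix 1) |
| Strategy in SAP 2.3.1 | Treatment policy | Hypothetical, missing at random |
| Value analysed | Observed | Imputed from own arm |

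SAP 9 lists non-compliance and protocol deviation among the reasons for study discontinuation, so the right-hand column is an anticipated route.

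**3. Size on SANDE Day 28.** Assume that removed active-arm subjects would have scored like vehicle, and that same-arm imputation returns the arm mean. With Δ the difference in the rest of the arm:
- treatment policy difference = (1 − w) × Δ + w × 0
- difference after same-arm imputation = Δ
- overstatement = w × Δ

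Removals from the vehicle arm add nothing under these assumptions.

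| w | Subjects of 230 | Overstatement, Δ = 8.3 | Overstatement, Δ = 7.9 |
|---|---|---|---|
| 1% | 2.3 | 0.083 mm | 0.079 mm |
| 2% | 4.6 | 0.166 mm | 0.158 mm |
| 5% | 11.5 | 0.415 mm | 0.395 mm |

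Standard error at 230 per arm = 17.72 × √(2/230) = 1.65 mm, and 0.415/1.65 = 0.25.

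Power for the smaller treatment policy difference at w = 5%, with 230 per arm: 99.8% for 8.3 × 0.95 = 7.885, and 99.5% for 7.9 × 0.95 = 7.505.

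**4. Primary endpoint.** The same formula gives an active rate of (1 − w) × 80% + w × 30%, which is 79.5% at w = 1% and 77.5% at 5%. The overstatement is 0.5 to 2.5 percentage points on a 50-point difference, with power above 99.9%. The vehicle-like assumption is hard to defend here. Site staff give the in-office drop at the Day 14 visit just before the post-drop test (Protocol 5.2, 7.2.3), so poor home dosing need not remove the response. The main effect is therefore lost observed data.

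**The case against.** The strongest reply is that nothing conflicts. SAP 2.3.1 treats poor compliance and withdrawal as separate intercurrent events and declares a strategy for each. That stands: a reader might infer that the SAP contradicts itself, and it does not. What remains is that, for a poor complier, a discretionary act can turn the first event into the second.

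A reader might also infer that poor compliers must be removed. The text does not say so. Protocol 6.10 is permissive, and Protocol 5.6 and SAP 12.1 require only that a deviation be recorded when vial counts fall outside 80% to 125%. Part of 6.10 also reads like a list of disposition reasons, since it includes death and loss to follow-up.

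Nor is every such loss preventable. A subject who does not attend yields no data for that visit, whether or not formally removed.

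The size rests on assumptions. No document gives the share removed, and subjects removed for a deviation or ineligibility may have been taking their drug. The SAP's abbreviation list includes fully conditional specification; if the imputation model conditions on earlier scores, poor early responders need not be imputed at the arm mean.

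Finally, Protocol 9.1.3 lists missing-as-failure, not-at-random imputation and other robustness analyses, and parts of the SAP's estimand and efficacy text are redacted. It cannot be concluded that no reference-based analysis of these withdrawals exists. Such analyses vary the assumption, however; they do not recover outcomes that were never measured.

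**Conclusion.** The point holds as a misalignment between data collection and estimand. Protocol 6.10 permits avoidable loss of efficacy data in subjects whose outcomes the treatment policy element is meant to capture, and the SAP then fills the gap with same-arm values.

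The consequence is small. With 1% to 5% of the active arm removed and vehicle-like outcomes, both assumed, SANDE Day 28 is overstated by about 0.08 to 0.42 mm, or 1% to 5% of 8.3. Someone might read this as a threat to the trial's conclusion or its power; the figures do not support that. The case for acting is that the loss can be reduced with visits and procedures already in the schedule.

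**What to change.** State in Protocol 6.10 that non-compliance, a protocol deviation or an eligibility finding after randomisation is recorded as a deviation and is not by itself a reason to end scheduled efficacy follow-up of a randomised subject who is willing to attend. State in SAP 2.3.1 that data so collected enter Estimand 1 as observed. Leave voluntary withdrawal, safety exits and all decisions on study drug as they are.

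For any subjects already removed for these reasons, report counts by arm, reason and timing relative to Days 14, 28 and 90. Add a sensitivity analysis that imputes them from the vehicle arm, unless the redacted text already contains one.

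Cost: a protocol amendment and a site memo, a few more scheduled visits by subjects who have already consented, and possibly a slightly smaller estimated effect. No new procedure is needed.

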#### 6.10.1 Actions after Discontinuation

Also see Early Termination Procedures (Section [7.3](#)).

All subjects who discontinue study intervention due to a report of an AE must be followed and provided appropriate medical care until their signs and symptoms have remitted or stabilized or until clinically meaningful abnormal laboratory findings have returned to acceptable or pre-study limits.

For subjects who choose to withdraw consent or who are discontinued for non-compliance prior to completing the study, every possible effort should be made by the Investigator to assure there is a final visit that includes all examinations listed for the Early Termination Visit.

### **6.10.2 Discontinuation of the Entire Study**

The entire study may be discontinued at any given site by the Investigator or the Sponsor or Sponsor representative, or at all sites by the Sponsor. Prompt, written notice of reasonable cause to all other relevant parties (Sponsor or Investigator) is required. Prompt notice to the IRB and to regulatory authorities is also required.

### **6.10.3 Completed Study**

The study is completed when the last visit of the last subject has been completed at the last site taking part in the study. The Sponsor or Sponsor representative will be in communication with the investigational sites regarding enrollment completion.

## **7. STUDY ACTIVITIES**

### **7.1 Screening and Run-In Period**

#### **7.1.1 Screening Visit (Day -14 [+3\* days])**

- Informed consent
- Demographics
- Medical, ophthalmic, and surgical history
- Prior or concomitant medication review
- Vital signs (heart rate and blood pressure)
- Urine pregnancy test (WOCBP only)
- Symptom Questionnaire (VAS) (Ocular Discomfort, Eye Dryness [REDACTED])
- SANDE Questionnaire (VAS)
- Corrected visual acuity
- Slit-lamp biomicroscopy
- At least 5-minute rest period

[REDACTED]

[REDACTED]

[REDACTED]

- [REDACTED]
- [REDACTED]
- [REDACTED]
- CAE exposure
- [REDACTED]
- [REDACTED]
- Inclusion and exclusion criteria
- AE Review
- Dispensing of the study intervention
- In office administration of study intervention by subject under site staff supervision
- Intraocular pressure
- Dilated fundus exam

\* The Baseline visit is requested to be scheduled between 11 and 14 days after the Screening visit. If absolutely necessary, the Baseline visit may be delayed up to 7 days (extending the run-in period to a maximum of 21 days).

## 7.2 Randomized Intervention Period

### 7.2.1 Baseline (Day 1) Procedures

- Collection of used and unused study intervention
- Concomitant medication review
- AE review
- Vital signs (heart rate and blood pressure)
- Urine pregnancy test (WOCBP only)
- Symptom Questionnaire (VAS) (Ocular Discomfort, Eye Dryness [REDACTED])
- SANDE Questionnaire (VAS)

- Corrected visual acuity
- Slit-lamp biomicroscopy
- [REDACTED]
- Inclusion and exclusion criteria review
- Randomization
- Dispensing of study intervention
- At least 30 and up to 45-minute rest period
- Pre-drop unanesthetized Schirmer test
- At least 15 and up to 20-minute rest period
- In office administration of study intervention by site staff
- Post-drop unanesthetized Schirmer test
- Hematology, chemistry, and urinalysis
- Intraocular pressure
- Dilated fundus exam

### 7.2.2 Day 7 ( $\pm$ 2 days) Procedures

- Concomitant medication review
- AE review
- Symptom Questionnaire (VAS) (Ocular Discomfort, Eye Dryness [REDACTED])
- SANDE Questionnaire (VAS)
  - [REDACTED]
  - [REDACTED]
- Corrected visual acuity
- Slit-lamp biomicroscopy
  - [REDACTED] [REDACTED]
  - [REDACTED]
  - [REDACTED]
  - [REDACTED]
  - [REDACTED]
  - [REDACTED]
- Pre-drop unanesthetized Schirmer test
- At least 15 and up to 20-minute rest period
- In office administration of study intervention by site staff
- Post-drop unanesthetized Schirmer test

### 7.2.3 Day 14 ( $\pm$ 2 days) Procedures

- Collection of used and unused study intervention
- Concomitant medication review
- AE review

- Symptom Questionnaire (VAS) (Ocular Discomfort, Eye Dryness [REDACTED])
- SANDE Questionnaire (VAS)
  - [REDACTED]
  - [REDACTED]
- Corrected visual acuity
- Slit-lamp biomicroscopy
  - [REDACTED]
  - [REDACTED]
  - [REDACTED]
  - [REDACTED]
  - [REDACTED]
  - [REDACTED]
- Dispensing of study intervention
- At least 30 and up to 45-minute rest period
- Pre-drop unanesthetized Schirmer test
- At least 15 and up to 20-minute rest period
- In office administration of study intervention by site staff
- Post-drop unanesthetized Schirmer test

#### 7.2.4 Day 28 ( $\pm$ 2 days) Procedures

- Collection of used and unused study intervention
- Concomitant medication review
- AE review
- Symptom Questionnaire (VAS) (Ocular Discomfort, Eye Dryness [REDACTED])
- SANDE Questionnaire (VAS)

- Corrected visual acuity
- Slit-lamp biomicroscopy
- [REDACTED]
- [REDACTED]
- [REDACTED]
- [REDACTED]
- [REDACTED]
- Dispensing of study intervention
- At least 30 and up to 45-minute rest period
- Pre-drop unanesthetized Schirmer test
- At least 15 and up to 20-minute rest period
- In office administration of study intervention by site staff
- Post-drop unanesthetized Schirmer

### 7.2.5 Day 60 ( $\pm$ 5 days) Procedures

- Collection of used and unused study intervention
- Dispensing of study intervention

## 7.2.6 Day 90 (-2 / +5 days) Procedures

- Collection of used and unused study intervention
- Concomitant medication review
- AE review
- Vital signs (heart rate and blood pressure)

- Urine Pregnancy test (WOCBP only)
- Symptom Questionnaire (VAS) (Ocular Discomfort, Eye Dryness [REDACTED])
- SANDE Questionnaire (VAS)
  - [REDACTED]
  - [REDACTED]
  - [REDACTED]
- Corrected visual acuity
- Slit-lamp biomicroscopy
  - [REDACTED]
  - [REDACTED]
  - [REDACTED]
  - [REDACTED]
  - [REDACTED]
  - [REDACTED]
  - [REDACTED]
- Pre-drop unanesthetized Schirmer test
- At least 15 and up to 20-minute rest period
- In office administration of study intervention by site staff
- Post-drop unanesthetized Schirmer test
- Hematology, chemistry, and urinalysis
- Intraocular pressure
- Dilated fundus exam
- Study Exit

### **7.3 Early Termination Procedures**

Every effort should be made to perform the following procedures at the Early Termination visit.

- Collection of used and unused study intervention
- Concomitant medication review
- AE review
- Vital signs (heart rate and blood pressure)
- Urine pregnancy test (WOCBP only)
- Corrected visual acuity
- Slit-lamp biomicroscopy
- Hematology, chemistry, and urinalysis
- Intraocular Pressure
- Dilated Fundus Exam
- Study Exit

### **7.4 Unscheduled Visits**

An unscheduled visit may be any visit to the Investigator other than the visits specified in the protocol as possibly required for the subject's ophthalmic condition.

The investigator will perform all procedures necessary to evaluate the study participant at these visits and record any AEs in the eCRF.

## **8. QUALITY CONTROL AND ASSURANCE**

The progress of the study will be monitored by on-site, written, and telephone communications between personnel at the Investigator's site and the Study Monitor. The Investigator will allow the Sponsor or designee and/or representatives of Health Regulatory Agencies to inspect all eCRFs, subject records (source documents), signed consent forms, study medication records (receipt, storage, preparation, and disposition), and regulatory files related to this study at mutually convenient times at regular intervals during the study and upon request after the study has been completed.

The purpose of these visits is to provide the Sponsor and/or Health Regulatory Agency the opportunity to evaluate the progress of the study, document compliance with the protocol and with regulatory requirements, verify the accuracy and completeness of subject eCRFs, resolve any apparent discrepancies or inconsistencies in the study records, and account for all investigational supplies.

## **9. PLANNED STATISTICAL METHODS**

### **9.1 General Considerations**

Quantitative variables will be summarized using number of subjects (n), mean, median, standard deviation (SD), minimum and maximum. Qualitative variables will be summarized using counts and percentages.

All summaries will be presented by treatment group.

For the purpose of summarization, medical history, concurrent medications, and AEs will be coded to MedDRA and WHO Drug dictionaries, as appropriate.

Baseline measures are defined as the last non-missing measure prior to the initiation of randomized study treatment unless otherwise defined in the SAP.

Change from Baseline (CFB) will be calculated as post-Baseline result – Baseline; treatment comparisons will be calculated as AR-15512 – vehicle.

All primary and secondary analyses will be two-sided at a significance level of 0.05.

#### **9.1.1 Unit of Analysis**

Safety endpoints will be analyzed for both eyes. For efficacy endpoints assessed at the eye level, the unit of analysis will be the “study eye” as defined in Section 9.1.2. For efficacy endpoints assessed OU, the unit of analysis will be the subject.

#### **9.1.2 Study Eye Selection**

The study subject must have at least one eye (the same eye) meeting all the inclusion criteria (Section 4.2) and none of the exclusion criteria (Section 4.3) at both Screening and Baseline visits where applicable. Study subjects will be dosed in both eyes. If both eyes are eligible at the time of randomization, the study eye will be defined as the eye with the lower pre-drop unanesthetized Schirmer score to be performed at the Baseline visit. If both eyes still qualify and have the same pre-drop unanesthetized Schirmer score, the right eye will be designated as the study eye.

### **9.1.3      Missing Data**

The primary analysis will be completed with available data per subject as specified in Estimand 1 from the intent-to-treat (ITT) population, assuming the overall study discontinuation rate is <5% in each arm. If the study discontinuation rate is  $\geq 5\%$  in each arm then the primary analysis will be based on multiple imputation methodology as specified in Estimand 2, and the available data analyses will become robustness analyses.

[figure not shown]
Additional robustness analyses will include repeating the primary analysis on the ITT population imputing missing data as failures for the proportion of subjects with  $\geq 10$  mm increase in unanesthetized Schirmer score on Day 14 endpoint; using multiple imputation methodology under different assumptions of missingness (at random and not at random) each using 30 imputed values; the ITT population imputing missing data using last observation carried forward (LOCF); the ITT population using trimmed means; and the per-protocol (PP) population with available data per subject.

### **9.1.4      Hypotheses**

The primary endpoints will be tested as follows:

$H_{01}$ : The difference between study eyes treated with AR-15512 (0.003%) and study eyes treated with vehicle, in the proportion of subjects with  $\geq 10$  mm increase in unanesthetized Schirmer score on Day 14 = 0.

$H_{11}$ : The difference between study eyes treated with AR-15512 (0.003%) and study eyes treated with vehicle, in the proportion of subjects with  $\geq 10$  mm increase in unanesthetized Schirmer score on Day 14  $\neq 0$ .

